### **7.4 Independent Physician Adjudicator**

An independent Physician Adjudicator (IPA) will be responsible for review and adjudication of all serious and potentially device-related adverse events, at minimum. Other events may be reviewed as defined in the IPA Charter.

In order to enhance objectivity and reduce the potential for bias, the IPA shall be independent of the Sponsor as well as the investigational sites and investigators. The methodology for performing these responsibilities shall be developed and outlined in the IPA Charter. Operational provisions shall be established to minimize potential bias.

## **8. Measures to Minimize Bias**

The following measures will be implemented to minimize the potential for bias in this single arm Registry:

- Sites are requested to screen and enroll consecutive subjects, as far as possible, and enrollment activities will be documented in a screening/enrollment log.
- Multiple sites will be included to ensure a representative sample of physicians performing the procedure and to provide a reasonable enrollment period.
- Site selection will be performed using predefined parameters to ensure Investigators are appropriately qualified to conduct registry.
- Site training will be performed to assure full understanding and engagement to comply with the study design and all protocol requirements.
- A sample of adverse events will be reviewed and assessed by an independent Physician.
- Any known or foreseeable factors that may compromise the outcome of the Registry or the interpretation of results are covered by the Inclusion and Exclusion criteria.
- Financial disclosures will be collected from all investigators to document any potential for bias or conflict of interest.

## 9. Risks and Benefits

### 9.1 Risk Analysis

Risks associated with the SCOUT® Surgical Guidance System are managed in accordance with ISO 14971, Medical Devices- Application of risk management to medical devices. Risks associated with localization devices are well-understood and have been documented in the risk analysis, published clinical literature, as well as post-market surveillance data available for the benchmark devices. The nature of the SCOUT® System procedure carries the same clinical risks to the intended patient population as other localization technologies. The risk analyses for these devices included objective reviews of published and available unpublished medical and scientific data. The sections below provide an overview of residual risks identified in the risk management reports and anticipated benefits of the medical device.

The safety and performance aspects of the SCOUT® System have been evaluated using risk analysis techniques. The risks associated with the use of the SCOUT® System are considered reasonable in comparison to the anticipated benefits to patients. There were no reports of morbidity/mortality attributable to use of the SCOUT® System in any study.

The risks associated with the SCOUT® System are the same as existing benchmark localization technologies used in the intended patient population, as such the SCOUT® System poses an acceptable level of risk for its intended use.

### 9.2 Anticipated Clinical Benefits

All information supplied with the SCOUT® System clearly indicates the intended purpose of the device, namely use as a localization system for the identification of a soft tissue biopsy site or soft tissue site intended for surgical removal. The intended clinical benefit of use of a localization system is to facilitate identification (e.g., location) of target tissue in patients medically indicated for excision of soft tissue due to suspected or confirmed carcinoma.

These same benefits were assessed for the SCOUT® device where the investigators concluded that the SCOUT® System is safe and effective for guiding the excision of palpable and non-palpable breast lesions and a viable alternative to standard localization options.

While there is no guaranteed clinical benefit associated with participation in this registry, it is expected that participants will have similar benefits as other commercially available localization systems. Compared to other available localization systems, registry participants may benefit from a streamlined clinical pathway resulting in reduced number of invasive procedures.

### **9.3 Anticipated Adverse Events and Adverse Device Effects**

The nature of the SCOUT® System procedure carries the same clinical risks to the intended patient population as other localization technologies. Namely anticipated ADEs included:

- infection- there have been no instances of reported infection from the reflector. Incidence of infection from other localization systems have been reported between 1.56-4.61%.
- adverse reaction to materials- Using the highest values (worst case observed), a total of approximately 0.0075 µg of nickel was released, from each device, over a 30-day period. This translates to about 0.00025 µg per day released per reflector . Nickel potentially released from the reflector is less than 0.0004% of nickel absorbed by adults during the normal course of each day. Complaint rates range from 0-0.02% annually with no adverse events associated.
- tissue/vascular trauma- Complaint rates ranges from 0-0.08% annually in the global market.
- inaccurate location detection- Complaint rates range from 0-0.48% annually in the global market.
- inaccurate deployment- complaint rates range from 0-0.22% annually in the global market.
- device migration-complaint rates range from 0-0.02% annually in the global market.

Risks associated with the SCOUT® System and localization procedure, together with their likely incidence, are described in the IFU.

There may be risks related to the device under investigation that are unknown at present. Likewise, the exact frequency of the risk may be unknown. However, the SCOUT® System has been commercially available and utilized extensively in the US market since 2014 (K141318) and Europe since 2020. The risks associated with the use of the SCOUT® System are considered reasonable in comparison to the anticipated benefits to patients. There were no reports of morbidity/mortality attributable to use of the SCOUT® System in any study.

Possible risks associated with participating in this registry are not anticipated to be any different from risks associated with undergoing procedures with the commercially available SCOUT® System (globally). Protocol required assessments are aligned with standard of care for treating non-palpable breast lesions using localization and as such do not pose any additional risks.

### **9.4 Steps Taken to Control or Mitigate Risks**

In-depth recommendations, special precautions and instructions regarding patient selection, device handling, and device placement are included in the IFU for the SCOUT® System. It is also stated in the IFU

that the devices can only be used by physicians who have received appropriate training on how to use the device. Physician users are expected to be aware of the known and foreseeable safety risks associated with the use of the device including the surgical and/or non-surgical treatment of these conditions.

Risks associated with the use of the device under investigation are minimized through device design, investigator selection and training, pre-specified participant eligibility requirements, and risk-based monitoring to ensure adherence to the protocol. All AEs will be reported to the Sponsor as summarized in Section 7.3 and will be monitored internally for safety surveillance purposes.

## **10. Quality Control & Quality Assurance**

### **10.1 Training**

Sponsor will ensure that Investigators and site staff are trained in the study protocol, including consent requirements and data collection procedures. Training may be completed by on-site visit or remote/web-based training. No additional device training or case support is required for Study Participation, device training will be in accordance with Merit requirements for commercial use applicable to the country where site is located.

Canadian sites are required to complete the Merit Medical Canada Training plan. Prior to use of the device, radiologists and surgeons will complete didactic and hands-on product training. Clinicians will complete proctor sign-off prior to enrolling participants in this registry.

US sites will be selected from established device users and no additional device training is required.

The Principal Investigator will be responsible for ensuring that all subsequent personnel involved in the study are trained and receive proctor sign-off, where applicable.

### **10.2 Quality Assurance**

The Sponsor will implement and maintain quality systems defined by written procedures to ensure that study is conducted and data are generated, documented and reported in compliance with this CIP, Good Clinical Practices (ISO 14155:2020) and the applicable regulatory requirements. Included in these procedures will be quality control measures to ensure that all data are reliable and have been processed correctly at each stage of handling.

The Sponsor will secure agreement with the Investigator to ensure direct access to the site and source data/documents and reports, for the purpose of monitoring and auditing by the Sponsor and/or regulatory authorities and/or REBs/IRBs.

### **10.3 Regulatory Inspections/ Audits**

The registry may be inspected by regulatory agencies or audited by the Sponsor. These inspections may take place at any time during or after the registry. In the event that audits are initiated by the Sponsor (or its designee) or national/international regulatory authorities, the Investigator must allow access to the original medical records and must provide all requested information. In the event that audits are initiated by a regulatory authority, the Investigator will immediately notify the Sponsor.

#### **10.4 Suspension or premature termination of the registry**

In the case that the registry must be suspended or prematurely terminated, investigational sites will be notified and arrangements will be made with the highest regard for participant safety.

### **11. Publication**

The registry will be registered in a publicly accessible database prior to participant inclusion, and the results of the registry will be made publicly available upon conclusion in accordance with the Declaration of Helsinki. At the conclusion of the registry, a report will be prepared for presentation and for publication. Authorship is based on the ICMJE (International Committee of Medical Journal Editors) guidelines.

All parties should adhere to accepted guidelines for ethical reporting. Negative and inconclusive as well as positive results must be published or otherwise made publicly available. Sources of funding, institutional affiliations and conflicts of interest must be declared in the publication.

2.1 Preface

SCOUT® has been identified as an alternative to other localization options, providing maximum flexibility in patient visit scheduling. In the COVID-19 era, it would follow that improved efficiencies, leading to a decrease in patient visits to the breast center, as well as reduced contact with the technicians prior to surgery, is the preferred treatment option for patient and clinician safety and reduced logistical burden. Taveh et al. showed that by deploying the SAVI SCOUT® at the time of tumor biopsy, the need for a second procedure to localize the tumor was eliminated, thus reducing the number of patient visits and potential COVID-19 exposure. The authors demonstrated that wireless localization using SAVI SCOUT® was an effective and time-efficient alternative to wire localization, resulting in excellent physician and patient acceptance. Parkinson et al. found insertion of SCOUT at biopsy resulted in at least one (1) less patient visit to the breast center.

This Canadian registry is intended to assess the utility of SAVI SCOUT® in the Canadian public healthcare system where there are limited resources and a conservative approach to patient and clinician exposure to harm (i.e., radiation, COVID-19 exposure, patient emotional trauma). By assessing the utility of reflector insertion at the time of biopsy, this study will be able to measure the impact on patient visits to the breast center for invasive procedures between biopsy and surgery, and quantify this value to the public healthcare system. The efficacy and safety of this system will be further assessed, as well as the acceptance of clinicians and patients.

2.2 Scope of the analyses

These analyses will assess the utility, performance and safety of SCOUT® device and will be included in the clinical study report.

Utility will be assessed based on the primary endpoint: The number of patient visits to the breast center for invasive procedures from the time of biopsy to surgery.

Performance will be assessed based on device success, procedural success, clinician assessment and participant satisfaction scores.

Safety will be assessed based on the rate of device-related adverse events.

3 Study Objectives and Endpoints

3.1 Study Objectives

Primary Objective: To demonstrate the utility of the SCOUT® Surgical Guidance system to improve workflow and efficiency in Canadian centers treating breast cancer.

Secondary Objective: To further evaluate the safety and performance of the SCOUT® Surgical Guidance system in 500 consented BI-RADS 4C/5 patients according to the instructions for use.

3.2 Endpoints

Primary Endpoint: The number of patient visits to the breast center for invasive procedures from the time of biopsy to surgery.

Secondary Endpoint:

1. Device success: percent successful localization, detection and retrieval;
2. Device safety: rate of device-related adverse events;
3. Procedural success: absence of close margins (DCIS: <2mm), positive margins (tumor on ink) or requirement for re-excision.
4. Duration (days) from assessment to surgery and biopsy to surgery;
5. Radiologist assessment: ease of placement; ability to position reflector in desired location; scheduling flexibility; visibility on ultrasound/ mammography (immediate and late); artifact (Tomo/MRI if applicable).
6. Surgeon assessment: ease of detection; ease of device retrieval.
7. Participant satisfaction questionnaire: anxiety; convenience; pain; overall experience compared to expectation
8. Process improvement with implementation of same-day biopsy and SAVI SCOUT® placement.

[figure not shown]
4 Study Methods

4.1 General Study Design and Plan

This is a single-arm, multicenter, non-randomized cohort study. This is a non-blinded study with no active control for this study. However, the primary endpoint will be compared to historical controls.

The registry is divided into three periods:

1. Inclusion Period: from registry eligibility screening until reflector insertion;
2. Device Period: from reflector insertion at biopsy to removal at surgery;
3. Outcomes Period: from completion of surgery to pathology report of outcomes.

4.2 Inclusion-Exclusion Criteria and General Study Population

This study will include five hundred (500) BI-RADS 4C/5 patients undergoing biopsy of a breast lesion at an investigative center.

The inclusion criteria are as follows:

1. Woman >18 years and < 80 years of age;
2. Classified as BI-RADS 4C or 5;
3. Lesion depth is < 6 cm from skin surface;
4. Non-palpable lesions;
5. Informed consent obtained.

The exclusion criteria are as follows:

1. Multicentric breast cancer;
2. Pregnant or lactating;
3. Known or suspected nickel-titanium allergy.

4.3 Randomization and Blinding

N/A

4.4 Study Assessments

	Consent*	Biopsy**	Surgery	Final Outcomes***
Patient Data				
Informed Consent	X			
Demographic information (age, height, weight, diagnosis)		X		
Neoadjuvant therapy (start and stop date)			X	
Device and Procedural Data				
Reflector insertion data (success, deployment within lesion or distance from lesion, depth of reflector, type of guidance used, number of reflectors used, type of lesion, reflector detection)		X		
Reflector detection (before incision or after incision)		X ⁱ	X	
Reflector retrieval (success, identification and retrieval duration)			X	
Operative time			X	
Adverse events (including device deficiencies)		X	X	

Scheduling Data				
Date of assessment		X		
Date of biopsy and insertion		X		
Date of surgery			X	
Satisfaction Assessments				
Radiologist assessment: ease of placement; ability to position reflector in desired location; scheduling flexibility; visibility on ultrasound/mammography; artifact (Tomo/MRI if applicable)				X ⁱⁱ
Surgeon assessment: ease of detection; ease of reflector removal				X ⁱⁱ
Participant satisfaction questionnaire			X ⁱⁱⁱ	
Pathology Report data				
Margins (positive; close <2mm; negative >2mm)				X
Re-excision required (after surgery)				X
Excised tissue volume/weight & specimen size				X

^{*}Performed prior to biopsy

^{**}Reflector insertion performed at time of biopsy

^{***}No additional participant visit; data recorded from pathology report

ⁱIf performed

ⁱⁱCollected once per clinician at completion of registry

ⁱⁱⁱWindow up to 2 weeks post-surgery (remote completion)

Identification of any number ranges for numeric endpoints along with their corresponding text descriptors.

- Continuous variables will be collected for: age, weight, height, operative time and adverse event rate, duration between events
- Categorical variables will be established for device success, procedural success, clinician assessment, participant satisfaction

5 Sample Size

No formal sample size calculation has been performed. Five hundred (500) participants will be included in this registry. This sample size has been selected to adequately support a multi-center experience reflective of the Canadian healthcare system and associated workflow.

Further, the Canadian Agency for Drugs and Technologies in Health (CADTH) assessed the evidence of STREAMLoc_Statistical Analysis Plan v1.0_30AUG2021

a competitive device and noted the requirement for a cohort size greater than 200 in order to draw conclusions of effectiveness.ⁱ It is estimated that this sample size will result in a robust Canadian data set.

6 General Analysis Considerations

6.1 Timing of Analyses

The final analysis will be performed after:

- All participants have completed the study and all assessment and outcome data is entered.
- Data monitoring is complete as per the monitoring plan and data clarification forms (DCF) have been resolved.
- The database has been locked.

6.2 Analysis Populations

A patient is considered enrolled in the registry as soon as they:

1. Have provided signed consent agreeing to be part of this registry; and
2. Undergo the insertion of the SCOUT® Reflector at the time of biopsy

Note- If a patient has given consent but the Reflector is not inserted at biopsy, the patient will not receive a participant number and will not be considered as enrolled in the registry. No patient data will be collected.

Participation in the registry will be considered complete after surgery, documentation of surgical outcomes and completion of the Participant Assessment Questionnaire. This will be documented on a study completion form. It is expected the duration of each participant will be approximately <7 months and will vary based on each participant's treatment plan.

6.2.1 Per Protocol Population

The per protocol (PP) population will include all consented participants in whom a SCOUT® Reflector has been inserted and who subsequently undergo breast surgery.

Endpoint analysis will be performed on the PP analysis set.

6.2.2 Intention-to-treat (ITT) Population

The ITT population includes all participants in whom the SCOUT® Reflector has been inserted. Any participants who have a reflector inserted and do not undergo surgery will be exited from the registry using a study completion form. The occurrence of this scenario is expected to be low ($\leq 10\%$). Reasons may include:

1. Benign concordant biopsy results.
2. Participant death prior to surgery due to metastases.
3. Lesion is metastatic from another location.
4. Participant declines surgery.

5. Participant is ineligible for surgery.

Descriptive data and adverse event analysis will be performed on the ITT analysis set. The PP and ITT endpoints will be calculated separately and compared. Differences between their results will be summarized and discussed.

6.2.3 Safety Population

Adverse events will be collected and analyzed for all events categorized as procedure or device-related for all enrolled participants between the point of inclusion to completion of surgery.

6.3 Covariates and Subgroups

Subset analysis will be performed for participants who have undergone neoadjuvant therapy (if applicable). Endpoints will be assessed separately and compared to the full cohort for safety, performance and utility.

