## 5. Data Analysis & Statistics

### 5.1 Sample Size Calculation

No formal sample size calculation has been performed. Five hundred (500) participants will be included in this registry. This sample size has been selected to adequately support a multi-center experience reflective of the Canadian and US healthcare system and associated workflow.

Further, the Canadian Agency for Drugs and Technologies in Health (CADTH) assessed the evidence of a competitive device and noted the requirement for a cohort size greater than 200 in order to draw conclusions of effectiveness. It is estimated that this sample size will result in a robust data set.

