### **5.3 Analysis of Clinical Data**

This registry is not hypothesis driven. The limitation of the design for this registry is that there are no pass/fail criteria from a statistical hypothesis testing.

Descriptive statistics will be generated for all endpoints using a 1-sided 95% confidence interval. Participant data will be quantified. For quantitative parameters, descriptive statistics will be reported: number, mean, standard deviation (SD), minimum, median and maximum values. For categorical variables, frequency and percentage will be reported. The primary endpoint will be compared to historical data using one-way analysis of variance.

Subset analysis may be performed for participants who have undergone neoadjuvant therapy.

Endpoint analysis will be performed on the PP analysis set. Descriptive data and adverse event analysis will be performed on the ITT analysis set.

Full analysis will be described in the statistical analysis plan and specified in the final report. No interim analysis is planned.

The Sponsor will perform data management and statistical analysis. Statistical analyses will be performed using the Statistical Analysis System (SAS) or other widely accepted statistical software.

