6.5.2 Analysis Methods to Minimize Bias

Endpoint data between sites will be assessed and compared to ensure there is no site-specific bias.

7 Summary of Study Data

Descriptive statistics will be generated for all endpoints using a 1-sided 95% confidence interval. Participant data will be quantified. For quantitative parameters, descriptive statistics will be reported: number, mean, standard deviation (SD), minimum, median and maximum values.

For categorical variables, frequency and percentage will be reported. The primary endpoint will be compared to historical data using one-way analysis of variance.

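### SAP 6.3 compares the neoadjuvant subset with a full cohort that contains it, so the displayed difference understates the neoadjuvant versus non-neoadjuvant difference by the subset's share

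*SAP*

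**What the plan says.** SAP 6.3 (Covariates and Subgroups) commits to a subset analysis of participants who underwent neoadjuvant therapy, where applicable, and states the comparison: "Endpoints will be assessed separately and compared to the full cohort for safety, performance and utility". It names no estimand, test or interval for it. Protocol 5.3 is weaker and names no comparator: "Subset analysis may be performed for participants who have undergone neoadjuvant therapy".

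The analysis sets decide who is in the cohort. SAP 6.2.1: "The per protocol (PP) population will include all consented participants in whom a SCOUT® Reflector has been inserted and who subsequently undergo breast surgery". SAP 6.2.2 defines the ITT set as everyone with a reflector inserted. Endpoints are analysed on PP, and descriptive data and adverse events on ITT. Neither set excludes neoadjuvant participants, and nothing in either document redefines the cohort as the remaining participants.

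On inference, protocol 5.3 says: "This registry is not hypothesis driven". SAP section 7 adds: "Descriptive statistics will be generated for all endpoints using a 1-sided 95% confidence interval". One-way analysis of variance is named only for the primary endpoint against historical data (SAP sections 7 and 8). SAP section 12 has a format for p-values but does not say which analyses will produce them.

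Neoadjuvant start and stop dates are among the data collected at surgery (protocol 4.7 and the assessment schedules in both documents).

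**The concern.** A subgroup comparison is meant to show whether the subgroup differs from everyone else. If the comparator includes the subgroup, part of the comparison is the subgroup against itself, and the displayed gap shrinks as the subgroup grows. The shrinkage always runs towards no difference and applies alike to safety, performance and utility. It needs no test; it is present in two descriptive columns set side by side.

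The sponsor singled this group out, presumably because it may behave differently. It is plausible that neoadjuvant participants keep the reflector longer, since it stays in from biopsy to surgery and protocol 5.2 says participation length varies with the treatment plan. That is an inference; neither document states it. If it is right, problems of late detection, migration or extra visits would show up in this group first.

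**Working it through.** **Inputs from the documents.** N = 500, without a formal calculation (protocol 5.1). Participants without surgery are expected to be at most 10% (SAP 6.2.2), so PP could be as small as 500 × 0.90 = 450. The comparator is the full cohort (SAP 6.3). The documents give no figure for this comparison, so there is none to reproduce.

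**Assumptions.** Neoadjuvant share p from 10% to 40%; equal variances, scaled to SD = 1; a two-sided 5% level; for one power example, a true difference of 0.3 SD. None of these is in the documents.

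**Step 1: attenuation.** The full-cohort mean is a weighted average:

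mean(full) = p × mean(neo) + (1 − p) × mean(rest)

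Subtracting from mean(neo) gives

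mean(neo) − mean(full) = (1 − p) × [mean(neo) − mean(rest)].

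This is an identity for means and proportions. It is not exact for medians or ratio measures.

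| Share p | Fraction of the difference displayed | Assumed rates 30% v 20% (10 points) appear as |
|---|---|---|
| 10% | 0.90 | 9 points |
| 20% | 0.80 | 8 points |
| 30% | 0.70 | 7 points |
| 40% | 0.60 | 6 points |

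**Step 2: what a naive two-sample procedure would do.** This applies only if such a procedure is used. With n1 = pN, treating the groups as independent gives variance 1/n1 + 1/N. The true variance of the overlapping contrast is 1/n1 − 1/N. For p = 20% and N = 500 (n1 = 100, rest = 400):

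- naive SE = √(1/100 + 1/500) = 0.1095
- true SE of the overlapping contrast = √(1/100 − 1/500) = 0.0894
- SE for disjoint groups = √(1/100 + 1/400) = 0.1118

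True size of the nominal 5% test: 1.96 × 0.1095 / 0.0894 = 2.40, two-sided tail 0.016.

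Power at 0.3 SD, overlapping: the expected contrast is 0.8 × 0.3 = 0.24, and (0.24 − 1.96 × 0.1095) / 0.0894 = 0.28, so power is about 0.61. Disjoint: 0.3 / 0.1118 − 1.96 = 0.72, so power is about 0.765.

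**Step 3: other shares.** The last column takes, at each share, the difference that the disjoint comparison detects with 80% power, and gives the power of the naive overlapping test for it.

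| Share p | Correlation of the two means, √p | True size of nominal 5% test | Naive power where disjoint has 80% |
|---|---|---|---|
| 10% | 0.32 | 0.030 | 73.7% |
| 20% | 0.45 | 0.016 | 65.6% |
| 30% | 0.55 | 0.008 | 55.2% |
| 40% | 0.63 | 0.003 | 42.4% |

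Simulation with 10,000 runs gave sizes of 0.032, 0.019, 0.007 and 0.002. At N = 450 the calculated sizes and powers are the same at equal share.

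**Step 4: separating the two effects.** With the correct overlapping variance the test statistic is 0.24 / 0.0894 = 2.68, identical to 0.30 / 0.1118 = 2.68 for disjoint groups. The loss of power in steps 2 and 3 therefore comes wholly from the naive SE. The attenuation in step 1 remains whichever SE is used.

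**The case against.** The best defence is that SAP 6.3 describes a display. It names no test, the registry is not hypothesis driven, and the SAP uses similar language elsewhere for nested groups: section 6.2.2 compares PP with ITT results although PP lies inside ITT, and section 7.3 looks at deviation-affected participants both separately and with the cohort. Subset against full cohort is also only a rescaled contrast. Given counts and means, a reader can recover the remainder as (N × full − n1 × subset) / (N − n1).

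Much of this stands. A reader might infer that the plan breaks an independence requirement and so loses power or mis-sizes a test. The documents do not support that: a descriptive side-by-side needs no independence, and no two-sample test is prescribed here. The size and power figures are conditional on an analyst choosing one. Even then the error is conservative. A reader might also take longer reflector dwell as established; it is not stated.

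What does not stand is that the descriptive reading removes the problem. The displayed gap is still (1 − p) of the one of interest, and asking readers to back-calculate the right comparator is a poor substitute for showing it. Nor is the plan free of inference: it promises confidence intervals for all endpoints and has a p-value convention, while leaving the method for this comparison open.

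**Conclusion.** As written, SAP 6.3 understates any neoadjuvant versus non-neoadjuvant difference in means or proportions by exactly the neoadjuvant share. That part needs no distributional assumption. Its practical size is unknown because the share is not given: a tenth of the difference at 10%, four tenths at 40%. The figures of 1.6% size and 61% against 77% power additionally assume a 20% share of 500, equal variances, a 0.3 SD difference and a naive two-sided 5% test that the SAP does not specify.

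The primary comparison with historical data is untouched, and the protocol treats the subset analysis as optional. This is a change that should be made because the stated comparator is the wrong one for the question and the remedy is nearly free. It does not put the registry's main result at risk.

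**What to change.** In SAP 6.3, replace the full cohort as comparator with participants who did not receive neoadjuvant therapy. Report each group and the difference between them with a confidence interval, and keep the full cohort as a descriptive reference column. State whether that interval is one- or two-sided, since the general rule in SAP section 7 is one-sided and gives no direction.

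Make the comparison in the PP set, where the surgery form records neoadjuvant dates. For the safety comparison in the ITT set, add a rule: participants who never reach surgery (up to 500 × 0.10 = 50 on the plan's own expectation) are shown as a separate group with status not recorded. Otherwise they would be counted as non-neoadjuvant by default.

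Align protocol 5.3, where the analysis is optional, with SAP 6.3, where it is firm.

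The cost is a few sentences in the SAP and one additional table column. PP endpoints need no new data. The SAP is version 1.0 of 30 August 2021 and the protocol is now version 3.0 of 21 February 2023, so the change can go into an update that brings the two into line.
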